4.4.3 Infusion Reactions

Nivolumab may cause severe or life threatening infusion-reactions including severe hypersensitivity or anaphylaxis. Signs and symptoms usually develop during or shortly after drug infusion and generally resolve completely within 24 hours of completion of infusion. Infusion-related reactions to copanlisib may also occur. Monitor patients for signs and symptoms of infusion-related reactions from the start of each infusion until at least 30 minutes after the end of the infusion, in an area containing resuscitation equipment and medications necessary for advanced life support and cardiopulmonary resuscitation. Toxicity management guidelines on drug-related infusion reactions are provided in **Table 5**.

Table 5 - Infusion Reaction Dose modification and Treatment Guidelines

NCI CTCAE Grade	Treatment	Premedication at Subsequent Dosing

Grade 1 Mild reaction; infusion interruption not indicated; intervention not indicated
	
Monitor vital signs as medically indicated until the participant is deemed medically stable in the opinion of the investigator.
	
Participant may be premedicated at least 30 minutes before infusion of nivolumab with:
 
Diphenhydramine 50 mg PO (or equivalent dose of antihistamine)
 
and/or
 
Acetaminophen 325-1000 mg PO (or equivalent dose of analgesic)


Grade 2 Moderate reaction; requires therapy or infusion interruption but responds promptly to symptomatic treatment (e.g., antihistamines, NSAIDs, narcotics, IV fluids); prophylactic medications indicated for ≤24 hrs
	
Stop Infusion.
 
Begin IV normal saline, and treat subject with diphenhydramine 50 mg IV (or equivalent) and/or acetaminophen 325-1000 mg; monitor subject until resolution of symptoms. Corticosteroid and/or bronchodilator therapy may also be administered as appropriate.
 
If symptoms resolve within 1 hour of stopping drug infusion, the infusion may be restarted at 50% of the original infusion rate. Otherwise dosing will be held until symptoms resolve and the participant should be premedicated for the next scheduled dose.
 
If symptoms recur, then no further nivolumab will be administered at that visit.
	
Participant may be premedicated at least 30 minutes before infusion of nivolumab with:
 
Diphenhydramine 50 mg PO (or equivalent dose of antihistamine).
 
and/or
 
Acetaminophen 325-1000 mg PO (or equivalent dose of analgesic).
 
If necessary, corticosteroids (up to 25 mg of SoluCortef or equivalent) may be used.

Grades 3 or 4
 
Grade 3: Severe reaction; prolonged (i.e., not rapidly responsive to symptomatic medication and/or brief interruption of infusion); recurrence of symptoms following initial improvement; hospitalization indicated for other clinical sequelae
 
Grade 4: Life-threatening; urgent intervention indicated
	
Stop Infusion.
 
Begin IV normal saline and treat as follows:
 
Investigators should follow institutional guidelines for the treatment of anaphylaxis.
 
Recommended bronchodilators, epinephrine 0.2-1 mg of a 1:1000 solution for SubQ or a 0.1-0.25 mg of a 1:10,000 solution injected slowly IV (or equivalent), as needed.
 
Subject should be monitored until symptoms resolve and the investigator is comfortable that the symptoms will not recur.
 
Participant is permanently discontinued from further study drug treatment.
	
No subsequent dosing

Appropriate resuscitation equipment should be available at the bedside and a physician readily available during the period of drug administration.
		

4.4.4 Additional Toxicity Monitoring and Prevention

4.4.4.1 Glucose and Diet Monitoring

Period	Fasting \geq 12 h required before first glucose measurement	Pre-dose glucose levels
Day 1 of Cycle 1	Yes	<125 mg/dL (non-diabetic patients) <160 mg/dL (diabetic patients)
Subsequent infusions after Cycle 1 Day 1	Yes	<160 mg/dL (fasting) <200 mg/dL (non-fasting)

Fasting refers to a \geq 12 hour fast. Non-fasting status includes any caloric intake such as meals, juice, snack, as well as other caloric intake not consistently called a meal.

From Cycle 1 Day 1 onwards, glucose measurements may be done either by laboratory analysis or in capillary blood.

Because of its inhibitory effect on the PI3K α -isoform, which is implicated in insulin metabolism, copanlisib infusions could be associated with a temporary increase in blood glucose. Addition of a meal in close proximity to copanlisib infusion may exacerbate glucose increase.

On infusion days a low calorie or low carbohydrate diet is recommended. It is recommended that timing and content of caloric intake as well as additional glucose testing (if clinically indicated) on infusion days is monitored by the investigators based on glucose response patterns during prior treatment days. Consultation with a diabetologist or endocrinologist is advised.

All glucose measurements, oral glucose lowering medication and/or insulin administration, if applicable, fasting/non-fasting status, and meal intake timing on infusion days will be collected as part of the clinical source documentation.

Glucose monitoring on study

Management of hyperglycemia and dose delay parameters are outlined in **Table 4**

The following assessments should be performed on Day 1, 8, and 15 of each cycle before receiving copanlisib unless otherwise specified:

- Patients should be fasting for at least 12 hours prior to the pre-dose glucose measurement. For details on fasting requirements and glucose measurement during C1D1 please refer to **Table 6**
- Blood glucose will be measured at 0 hours (pre-dose) and 1 hour after completion of copanlisib (+/- 15min) infusion. If 1 hour post-infusion blood glucose is \geq 35 mg/dL higher than pre-dose level, recheck in another hour (2 hours post-infusion) to ensure decline in blood glucose. Additional measurements to be performed as clinically indicated.

NOTE: If patient needs to take a low glycemic meal, then glucose test should be taken prior to meal intake.

- Prior to first cycle, patients should be educated on the signs and symptoms of hyperglycemia, such as frequent urination, increased thirst, blurred vision, headaches and difficulty concentrating and must report these to the investigator or their physician immediately.

4.4.4.2 Blood pressure measurement on treatment days

Blood pressure will be measured every 5 – 10 minutes prior to each copanlisib dose (no more than 4 measurements) until there are two consecutive results < 150/90 mmHg. If blood pressure is \geq 150/90 mmHg, the investigator can consider a medical intervention or delaying the infusion of study drug. The patient should rest for 5-10 minutes before next blood pressure is recorded.

On infusion days, blood pressure will be measured at 0 h (pre-dose), 30 min (mid-infusion), 60 min (end of infusion), and 1 h and 2 hours after the end of copanlisib infusion

Note: a window of \pm 15 min is allowed for all BP measurements, except for the 0 h (pre-dose) measurement, which may happen any time prior to infusion on the day of treatment.

4.4.4.3 Hyperlipidemia monitoring

Measurements for cholesterol, LDL and triglycerides.

Total cholesterol, LDL and triglycerides will be tested only at Screening, on Day 1 of every 2nd cycle starting from Cycle 2, and at the EOT visit. On these dates patients must be fasting prior to sampling according to local standards. If a patient can't adhere to fasting requirements, the evaluation of lipid-panels including triglycerides is considered not feasible.

Management of hyperlipidemia

As lipids are monitored for the duration of this study it is recommended to treat significant deviations from normal range with standard interventions and therapy in standard doses according to local medical practice. Goals of therapy are to keep fasting triglycerides < 300 mg/dL (3.4 mmol/L) and low-density lipoproteins (LDL) < 190 mg/dL (4.9 mmol/L) (lower LDL depending on cardiovascular risk) in patients with a life expectancy >1 year. The goals for fasting triglycerides can be raised to < 500 mg/dL (5.6 mmol/L) for patients with life expectancy <1 year (31).

Although there is a paucity of data on the effects of hyperlipidemia and cancer outcomes, these goals have been chosen to decrease risk of established complications of hypertriglyceridemia (pancreatitis) and hypercholesterolemia (cardiovascular events). For evaluation of lipid-panels including triglycerides the patient would be required to be fasted for 11 hours prior to sampling. For patients who cannot adhere to these fasting requirements the evaluation of lipid-panels including triglycerides and determination of

treatment is considered as not feasible

4.4.4.4 Opportunistic Infection (OI) Monitoring

In addition to the weekly clinical review and laboratory tests outlined in the schedule of assessment, the following should be performed in all patients prior to IV infusion of copanlisib:

- Evaluation of any new onset or worsening of pulmonary symptoms (i.e. cough, dyspnea or fever) that includes a lung examination at each visit prior to infusion
- Labs: WBC, Lymphocyte count, CD4 (for patients with signs of infection), blood cultures (per local SOC if patient develops febrile neutropenia or ANC CTCAE of grade 4), PCR for CMV (monthly for first 6 months of treatment and every 3 months thereafter)
 - Note: If PCR test for CMV > 500 IU/mL, treatment should be delayed until level reduces to \leq 500 IU/mL. Treatment of CMV should be initiated based on local SOC. Re-treatment with copanlisib will be allowed without dose reduction once PCR test for CMV is \leq 500 IU/mL.

Enhanced monitoring when prior medical history or laboratory parameters could be associated with one of the following risk factors:

- Intensive chemotherapy (\geq 2 lines of myelosuppressive cytotoxic therapy)
- History of CMV, herpes
- History of lower respiratory tract infection, history of immunodeficiency in the last 12 months
- Lymphocytes count < 500 while on treatment in clinical study

For patients with identified risk factors and those who developed OI, additional assessments will include:

- CD4 and CD8 count and ratio, CRP, blood cultures
- Any additional laboratory and diagnostic methods according to local SOC reported as unscheduled laboratory and diagnostic methods of assessment
- Radiological imaging (i.e. CXR or CT Scans)

Note: Treatment of developed OI should be based on local standards of care (SOC).

Prophylaxis of OI

Mandatory prophylactic therapy is not recommended in all patients:

- Review of Copanlisib data do not support risk benefit ratio favoring prophylaxis in all patients
- Mandatory prophylaxis may cause a higher risk of side effects associated with supportive treatment where no risks factors are present
- Currently implemented schedule of assessment, and additional enhancements provide frequent monitoring and flexibility for prophylaxis based on local SOC

Although not mandated in all patients, OI prophylaxis may be initiated at the discretion of the treating investigator's judgment of the benefit/risk ratio in any patient, irrespective

of whether a high-risk feature is present, per local SOC. If so, treatment, dosage and route of administration must be reported as concomitant medications.

Prophylactic treatment of OI should be initiated based on SOC in patients when high risk factors are identified (see above risk factors). For example: Bactrim or equivalent, Acyclovir or equivalent. Treatment, dosage and route of administration must be reported as concomitant medications.

4.4.5 Prohibited and Restricted Therapies

Participants are prohibited from receiving the following therapies during the Screening and Treatment Phase (including retreatment for post-complete response relapse) of this trial:

- Any non-study anticancer or immunotherapy agent
- Any non-study investigational agents
- Radiation therapy
 - Note: Radiation therapy to a symptomatic solitary lesion or to the brain may be allowed at the investigator’s discretion.
- Live vaccines within 30 days prior to the first dose of study treatment and while participating in the study. Examples of live vaccines include, but are not limited to, the following: measles, mumps, rubella, varicella/zoster, yellow fever, rabies, BCG, and typhoid vaccine. Seasonal influenza vaccines for injection are generally killed virus vaccines and are allowed; however, intranasal influenza vaccines (e.g., FluMist®) are live attenuated vaccines and are not allowed.
- Systemic glucocorticoids for any purpose other than to modulate symptoms from an adverse event of suspected immunologic etiology. Steroid treatment should be completed at least 14 days prior to resuming study-related treatments. The use of physiologic doses of corticosteroids may be approved after consultation with the Protocol Chair.
- Strong inhibitors or inducers of CYP3A4/5 (see **Table 7** below for examples)
- Medications that carry a strong risk for QT prolongation
- Herbal medications/preparations except for vitamins (see **Table 7** below for examples)
- Anti-arrhythmic therapy other than beta blockers or digoxin

Table 7: List of prohibited medications during the study

Category	Drug name
Strong CYP3A Inhibitors	Voriconazole, boceprevir, clarithromycin, cobicistat, conivaptan, danoprevir/ritonavir, eltegravir/ritonavir, grapefruit juice, indinavir/ritonavir, itraconazole, ketoconazole, lopinavir/ritonavir, mibefradil, nefazodone, nelfinavir, posaconazole, ritonavir, saquinavir, saquinavir/ritonavir,

	telaprevir, telithromycin, tipranavir/ritonavir, troleandomycin,
Strong CYP3A Inducers	Avasimibe, carbamazepine, mitotane, phenobarbital, phenytoin, rifabutin, rifampin (rifampicin), St. John's wort (hypericum perforatum)
Herbal Preparations/ Medications	Herbal preparations/medications are prohibited throughout the study. These herbal medications include, but are not limited to: St. John's wort, Kava, ephedra (ma huang), ginkgo biloba, dehydroepiandrosterone (DHEA), yohimbe, saw palmetto, and ginseng. Patients should stop using these herbal medications 7 days prior to first dose of study drug

Participants who, in the assessment by the investigator, require the use of any of the aforementioned treatments for clinical management should be removed from the study. All treatments that the Investigator considers necessary for a participant's welfare may be administered at the discretion of the Investigator in keeping with the community standards of medical care. The final decision on any supportive therapy or vaccination rests with the investigator and/or the participant's primary physician. However, the decision to continue the participant on study treatment requires the mutual agreement of the investigator, the Sponsor and the participant.

There are no prohibited therapies during the Post-Treatment Follow-up Phase.

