All subjects may continue in the treatment period until discontinuation due to disease progression, unacceptable toxicity, subject withdrawal, or study closure. Complete criteria for removal from treatment are found in **Section 4.5**.

[figure not shown]
[figure not shown]
[figure not shown]
Subjects will undergo end-of-treatment (EOT) evaluations at the time it is determined they will

be discontinuing study treatment. All subjects will be followed for at least 30 days after their last dose of study drug for the development of AEs. SAEs that occur within 100 days of the last infusion of nivolumab or before initiation of a new antineoplastic treatment should also be followed and recorded. Complete information on safety reporting can be found in **Section 5**.

After completion of treatment and EOT assessments, all subjects will continue to be followed every 3 months by telephone, e-mail, or optional clinic visit until death, withdrawal of consent, or closure of study. Information on survival and new cancer therapies will be collected. Subjects that discontinue treatment for reason other than disease progression may also continue to be monitored by radiologic imaging every 10 weeks until start of a new anti-cancer therapy, disease progression, death, withdrawal of consent, or the close of the study, whichever occurs first.

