4.5 Duration of Therapy and Criteria for Removal from Study Treatment

In the absence of treatment delays due to adverse event(s), treatment may continue indefinitely until one of the following criteria applies. The reason for study treatment removal and the date the patient was removed must be documented in the Case Report Form.

A participant must be discontinued from study treatment but continue to be monitored in the study follow-up for any of the following reasons:

- The participant or participant's legally acceptable representative requests to discontinue study treatment
- Confirmed radiographic disease progression outlined in **Section 9** and **Appendix E**
 - As immunotherapy has been shown to cause pseudo-progression, patients are eligible to remain on study after progression if they are clinically stable, if they desire and their treating physician agrees it is in the interest of the patient. If subsequent imaging confirms progression, the patient's date of progression will be the date of first progression
- Clinical progression or deterioration

- Progression or recurrence of any malignancy, or any occurrence of another malignancy that requires active treatment
- Unacceptable adverse experiences as described in **Section 4.4.2** Exceptions must be approved by the IND Sponsor.
- The participant has a medical condition or personal circumstance which, in the opinion of the investigator and/or sponsor, placed the participant at unnecessary risk from continued administration of study treatment.
- Investigator's decision to withdraw the subject
- The participant has a confirmed positive serum pregnancy test
- Noncompliance with study treatment or procedure requirements

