4.7 Duration of Follow Up

Subjects who discontinue from treatment should continue to follow up with their primary oncologist and be contacted every 3 months (+/- 2 weeks) to monitor OS for up to 3 years or death, whichever occurs soonest. Effort should be made to collect information regarding disease status until the start of new anti-neoplastic therapy, disease progression, death, or end of study. Information regarding post-study anti-neoplastic treatment will be collected if new treatment is initiated.

Subjects who are discontinued from the study treatment due to an unacceptable drug-related AE will be monitored for safety until the resolution of the AE to \leq grade 1, or stabilization, or until initiation of a new therapy for their cancer, whichever occurs first.

All subjects will be followed for at least 30 days after their last dose of study drug for the development of AEs. SAEs that occur within 100 days (+ 14 day reporting window) of the last infusion of nivolumab or before initiation of a new antineoplastic treatment should also be followed and recorded.

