10. HDL, LDL, triglycerides, total cholesterol; performed at Screen and Day 1 of every other cycle (starting at Cycle 2)
11. If TSH is abnormal, T3 and FT4 will be assessed.
12. Patients with positive tests for HBsAg or HIV are excluded from study. Patients with positive test for anti-HCV antibody will be eligible if they are negative for HCV-RNA. These patients should perform HCV RNA test with PCR monthly through treatment and 6 months thereafter. If viral load becomes positive, patient should be withdrawn from the study.
13. CMV PCR may be done up to 7 days prior to each Day 1 visit. CMV PCR should be done with

every cycle through cycle 6, then every 3 cycles thereafter.

14. Serum or urine pregnancy test required for WOCBP only. If urine pregnancy results cannot be confirmed as negative, a serum pregnancy test is required.
15. Bilirubin, hemoglobin, glucose, ketones, leukocytes, nitrite, pH, color, protein, RBC and WBC count, and specific gravity. Performed at baseline and Day 1 of every other cycle (starting at cycle2).
16. Labs and research blood should be collected within a window of 3 days prior to dosing. Labs may be repeated prior to dosing if needed.
17. MUGA scan or echocardiogram to measure LVEF; the method chosen at baseline must be the same throughout the whole study period (baseline and EOT); at EOT visit must be done if not previously done within 4 weeks.
18. Radiologic evaluations and tumor measurements will be performed at baseline (within 28 days of dosing), prior to each odd cycle (up to 1 week prior), and at End of Treatment visit. If patient comes off study for reasons other than disease progression, subject may have additional radiologic evaluations every 8 weeks until progression or start of new anti-cancer therapy. CT of the chest/abdomen/pelvis with contrast will be used, however, non-contrast CT chest and MRI abdomen/pelvis will be done for patients with contrast allergies.
19. Biopsy to be collected at baseline and 6 weeks after first dose of study drug (\pm 3 days, but before Cycle 2 Day 15 study drug). An optional biopsy may be performed at the time of progression. Approximately 6 core biopsy specimens will be obtained at each biopsy. Tumor biopsy will not be performed if the tumor is not accessible or if biopsy is considered not in the patient's best interest.

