11.2 Statistical Analyses

Data will be summarized descriptively within each phase overall and by subgroups of interest (e.g. cohort). The descriptive summary including demographics and baseline variables will include counts and percentages for categorical variables and means, medians, standard deviations, and quartiles for continuous variables.

ORR at 6 months, the primary outcome for Phase II, will be summarized using counts and percentages. Logistic regression will be used to compare the ORR between the two cohorts as well as to identify risk factors associated with ORR. Other binary outcomes (e.g. disease control at 6 months (SD+PR+CR) and immunologic response) will be analyzed using the same methods.

Time to event outcomes include overall survival (OS) and progression free survival (PFS). Overall survival is defined as the time from the first dose until death. Individuals without an event will be censored at the date of last contact. Progression free survival is defined as the time from the first dose until progression or death. Individuals who die will be counted as having progressed. Individuals without an event will be censored at the date of the last evaluation for progression. Kaplan-Meier curves will be used to graphically summarize the survival function and to estimate the median time to event and the proportion event-free at key intervals (e.g. 6 months) along with 95% confidence intervals. Cox proportional hazards models will be used to compare Cohorts A and B and to identify risk factors associated with OS and PFS. Graphical techniques (e.g. log-log plots) and formal statistical testing (e.g. Schoenfeld tests) will be used to assess the proportional hazards assumption. If necessary, alternate models (e.g. incorporating a time variable) will be considered.

Safety will be monitored continuously throughout the study, including the phase II component. Weekly team meetings and a minimum of monthly investigator calls will be conducted to review ongoing and resolved toxicity.

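### Section 4.4.5 and calendar footnote 12 remove or withdraw patients from the study, against the follow-up rules in 1.5, 4.5 and 4.7; applied literally, this could bias OS and, for some triggers, PFS

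*Combined protocol and SAP*

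**What the plan says.** Two rules take a patient out of the study:

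- Section 4.4.5, closing paragraph: participants who, in the investigator's assessment, "require the use of any of the aforementioned treatments for clinical management should be removed from the study".
- Footnote 12 of the Phase I and Phase II calendars (8.1 and 8.2), for patients who enter antibody-positive but HCV-RNA-negative: "If viral load becomes positive, patient should be withdrawn from the study". The RNA test is monthly during treatment and for 6 months after it.

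Three rules keep patients in follow-up:

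- Section 1.5: "all subjects will continue to be followed every 3 months by telephone, e-mail, or optional clinic visit until death, withdrawal of consent, or closure" of the study.
- Section 4.7: "Subjects who discontinue from treatment should continue to follow up with their primary oncologist and be contacted every 3 months".
- Section 4.5: "A participant must be discontinued from study treatment but continue to be monitored in the study follow-up for any of the following reasons". The list that follows names neither the need for a prohibited therapy nor HCV viremia. It does have general items: investigator decision, a medical condition that makes continued treatment an unnecessary risk, and noncompliance.

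For the analysis, 11.2 says of OS: "Individuals without an event will be censored at the date of last contact". For PFS the censoring date is the last evaluation for progression. Section 11.2 has no rule for patients removed from the study or given a prohibited therapy.

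**The concern.** A site cannot both remove a patient from the study and contact that patient until death. Some therapies on the 4.4.5 list (non-study anticancer agents, radiation, systemic steroids) may be needed because the disease is worsening. If follow-up stopped at that moment, the patient would be censored shortly before an event, and Kaplan-Meier and Cox analyses assume that censoring carries no such information. OS and PFS are secondary endpoints, to be compared between Cohorts A and B with 21 patients each, so a few patients lost this way would show. Survival data not collected at the time may not be recoverable later.

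**Working it through.** **1. The primary design, as a check on scope.** The documents give no sample size or power for OS or PFS; the only design figures are for ORR. Inputs from 11.1: 12 patients in stage 1, stop if there are no responders, 9 more patients, success if at least 3 of 21 respond. With X ~ Bin(12, p) and Y ~ Bin(9, p):

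P(success) = 1 − P(X=0) − P(X=1)·P(Y≤1) − P(X=2)·P(Y=0)

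- p = 0.05: 1 − 0.54036 − 0.31698 − 0.06226 = 0.0804 (stated 0.08)
- p = 0.20: 1 − 0.06872 − 0.08993 − 0.03805 = 0.8033 (stated 0.80)

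Both reproduce. Under 9.1 only withdrawal of consent before re-evaluation takes a treated patient out of the response denominator, so removal under 4.4.5 or footnote 12 leaves this design as it is.

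**2. Can study be read as study treatment throughout?** Not in footnote 12. It orders RNA tests for 6 months after treatment ends. For a positive result in that window there is no treatment left to stop, so withdrawal can only mean leaving follow-up. In 4.4.5 the reading is open: the same paragraph uses the study for removal and study treatment for the decision to continue.

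**3. Which endpoint is exposed, by trigger, if the literal rule is applied.**

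- *Non-study anticancer therapy.* Under 1.5 and footnote 18, off-treatment imaging ends when a new anticancer therapy starts. PFS follow-up is therefore cut in any case, and the added loss is mainly in OS.
- *Radiation or steroids outside the permitted uses.* OS and PFS are both exposed when the need reflects progression.
- *Live vaccines, herbal products, CYP3A4 drugs, anti-arrhythmics, HCV viremia.* No clear link to tumor prognosis, so censoring here need not be informative.

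**4. Illustration of size.** The event-time medians, the share removed (q) and the removal timing are all assumptions. The simulation used 400,000 patients with exponential event times. A share q was removed at a time uniform over the second half of the patient's own event time, and survival was estimated by Kaplan-Meier.

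| Endpoint, assumed median | True | q = 5% | q = 10% | q = 20% |
|---|---|---|---|---|
| 6-month PFS, 2 months | 12.5% | 13.4% | 14.5% | 17.1% |
| 6-month PFS, 4 months | 35.4% | 36.8% | 38.5% | 42.2% |
| 12-month OS, 6 months | 25.0% | 26.5% | 28.1% | 31.4% |
| 12-month OS, 10 months | 43.5% | 45.2% | 46.9% | 50.6% |

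The excess runs from 13.4 − 12.5 = 0.9 to 42.2 − 35.4 = 6.8 points for PFS, and from 26.5 − 25.0 = 1.5 to 50.6 − 43.5 = 7.1 points for OS. In a cohort of 21, q of 5% to 20% is 21 × 0.05 = 1.05 to 21 × 0.20 = 4.2, or about 1 to 4 patients. When the removal time was drawn from another patient's event time, so that it was unrelated to prognosis, estimates stayed within about 0.2 points of the truth.

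**The case against.** The strongest reply is that the protocol uses study loosely and plainly intends to follow everyone. Footnote 18 allows scans in patients who have come off study. Section 4.5 speaks of remaining on study after progression when it means staying on treatment. Section 4.4.5 itself adds that no therapy is prohibited in post-treatment follow-up, which presumes that patients may receive such therapy while still followed. The general items in 4.5 could cover both triggers with follow-up continuing, and the calendars already have a row for survival status and later anticancer therapy. Much care for worsening disease is also permitted: some radiation (4.4.5, 4.4.6), short steroid courses (4.4.6), and clinical deterioration as its own reason in 4.5.

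This stands as evidence that intent is ambiguous and that many sites would keep following these patients. It does not remove the contradiction: footnote 12 cannot mean treatment after treatment has ended, and a site that follows 4.4.5 to the letter has a written instruction to end participation.

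A reader might go further and infer that the protocol does drop these patients, so that OS and PFS will be inflated, perhaps unequally between cohorts. The documents do not support that. The follow-up rules point the other way, several triggers have no clear link to prognosis, and both cohorts share the same regimen and rules, with no stated reason for removals to differ.

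**Conclusion.** The contradiction is real and should be corrected; its effect on the results is conditional. Bias arises only if a site applies the literal wording and only for triggers that reflect worsening disease. It would then be upward for OS, and upward for PFS where the trigger is not new anticancer therapy. The documents do not allow its size to be derived. The figure of roughly 1 to 7 percentage points rests on an assumed 5% to 20% of patients being removed in the second half of their event time, which is a deliberately unfavorable pattern. It shows that the loss would matter in a cohort of 21; it is not a forecast. The affected endpoints are secondary, and the primary ORR and its stated error rates are untouched.

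**What to change.** Reconcile the passages. In 4.4.5 and in footnote 12 of both calendars, state that these events do not end study follow-up, and that survival contact and progression follow-up continue under 1.5, 4.5 and 4.7. Reserve removal from the study for withdrawal of consent. Which events should stop treatment is not judged here.

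A useful addition is a sentence in 11.2 saying how PFS treats prohibited or new anticancer therapy, with a sensitivity analysis, because off-treatment imaging is optional and stops at new therapy even after the wording is corrected.

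The cost is a few lines in an amendment. The follow-up contacts are already planned, so no new visit or procedure is needed.
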